#### **4.2 Registration Process for DF/HCC Institutions**

Applicable DF/HCC policy (REGIST-101) must be followed.

#### **4.3 General Guidelines for Other Investigative Sites**

Eligible participants will be entered on study centrally at DF/HCC by the Study Coordinator. Following registration, participants should begin protocol therapy within 7 days. Issues that would cause treatment delays should be discussed with the Sponsor-Investigator. If the subject does not receive protocol therapy following registration, the subject must be taken off study in the CTMS (OnCore) with an appropriate date and reason entered.

#### **4.4 Registration Process for Other Investigative Sites**

To register a participant, the following documents should be completed by the participating site and e-mailed to the Coordinating Coordinator:

- Current IRB approved informed consent document informed consent document signed by participant and investigator. Participant name and MRN must be redacted. Please ensure the participant's initials are written on each page of the informed consent document.
- HIPAA authorization form (if separate from the informed consent document)
- Signed and dated Eligibility Checklist
- The following source documentation is required:
  - Documentation of prior treatments/procedures performed to treat RCC
  - Reports documenting disease status
    - Chest CT
    - CT or MRI Abdomen and Pelvis
    - Tc99m Bone Scan
  - Pathology Report
  - Concomitant medication list
  - Progress note or equivalent documentation of consenting visit
  - Progress note documenting medical history and oncologic history
  - Screening Labs
  - Screening visit note with vital signs, weight, height, ECOG performance status, physical examination

The participating site will then e-mail the Coordinating Coordinator to verify eligibility. The Study Coordinator will follow DF/HCC policy (REGIST-101) and register the participant on the protocol. The Study Coordinator will fax or e-mail the participant study number, and if applicable the dose treatment level, to the participating site. The Study Coordinator will also contact the participating site and verbally confirm registration.

## 5. TREATMENT PLAN

### 5.1. Treatment Regimen

Protocol treatment must start within 7 calendar days of enrollment. All study therapy will be administered on an outpatient basis. Unless otherwise specified, treatment delay of more than 28 days from date of last intended therapy will result in treatment discontinuation. For combination therapy regimens, a new cycle will not start until atezolizumab and/or abemaciclib are given. No minimum time interval is required between abemaciclib and atezolizumab administration. Vomited should be skipped, and abemaciclib dosing resumed at the next scheduled dose. If a dose is missed, it may be taken when remembered if there are at least 6 hours before the next scheduled dose. Held doses of atezolizumab or abemaciclib will be considered omitted for that cycle.

**Table 1. ARM A Treatment**

ARM A - Regimen Description					
	Prophylaxis Details & Precautions	Starting Dose	Route	Schedule	Cycle Length
Abemaciclib	Refer to Table 20 for diarrhea supportive care and management guidance.	200mg BID	Oral	Days 1-21	21 Days

**Table 3. ARM C Treatment**

ARM C - Regimen Description Initial 5 patients					
	Prophylaxis Details & Precautions	Starting Dose	Route 	Schedule	Cycle Length

Atezolizumab	Consult with study PI regarding use of corticosteroids.  G-CSF/GM-CSF is prohibited.	1200mg	IV over 60 (+/-5) minutes  If the first infusion is tolerated, subsequent infusions may be administered over 30 (+/-5) minutes.	Day 1	21 Days
Subsequent 16 patients					
Abemaciclib	Refer to Table 20 for diarrhea supportive care and management guidance.	200mg BID	Oral	Days 1-21	21 Days

Based on results of Bayesian toxicity monitoring, the starting dose of abemaciclib may be subsequently modified to a lower dose level.

Infusion times may be extended as needed for safety (e.g., infusion reaction occurs). These instances must be documented in the patient medical records.

Local intervention is discouraged unless medically unavoidable. Radiation therapy to the thorax (including to lungs/pleura, esophagus, intrathoracic lymph nodes, C7-L2 vertebrae, or ribs) is not permitted while on study and is strongly discouraged for at least 90 days after the last dose of abemaciclib and atezolizumab (whichever is later) unless for medical emergency such as impending spinal cord compression after approval in each individual case by Sponsor-Investigator. Palliative radiation to a symptomatic solitary lesion/area outside the thorax may be considered on a case-by-case basis and only after consultation with the Sponsor-Investigator. Subjects receiving local intervention (e.g., palliative radiation) are allowed to continue to receive study treatment at the treating investigator's discretion.

## 5.2. Pre-Treatment Criteria

Pre-treatment assessments should be performed within 72 hours of planned treatment dose. Results from the patient's complete blood counts and serum chemistry must be reviewed prior to drug dosing. Study agents must be dispensed or administered only to subjects enrolled in the study and in accordance with the protocol. Standard institutional procedures for administering an oral agent via by mouth will be followed. An adequate supply will be provided with instructions on home administration.

### 5.2.1. Cycle 1, Day 1

The patient's laboratory parameters must meet eligibility criteria (section 3.1.9) to initiate cycle 1 day 1 of trial therapy. Transfusion or growth factors are not permitted between screening up to and including cycle 1 day 1 to re-meet eligibility criteria except for

patients assigned to atezolizumab monotherapy in Arm C for whom red blood cell transfusion to meet eligibility criterion for hemoglobin is permitted.

#### 5.2.2. Subsequent Cycles

Eligibility to receive subsequent doses is based on dose delay/modification criteria detailed in Section 6.

### 5.3. General Concomitant Medication and Supportive Care Guidelines

The treating investigator should discuss any questions regarding concomitant medications or treatments with the Sponsor-Investigator. The final decision on any supportive therapy or vaccination rests with the treating investigator. However, the decision to continue the subject on trial therapy or vaccination schedule requires the mutual agreement of the Sponsor-Investigator, treating investigator, and subject.

**The following medications and treatments are prohibited while the patient is receiving protocol therapy:**

- Any non-protocol antineoplastic therapy (radiation, chemo-, immuno- or biologic therapy)
- Other investigational agents
- Herbal products known to decrease PSA levels (e.g., Saw Palmetto, PC-SPES)
- Neulasta® and other granulocyte colony stimulating factors
- Live, attenuated vaccines (e.g., FluMist®) are prohibited within 4 weeks prior to initiation of study treatment, during treatment with atezolizumab, and for 5 months after the last dose of atezolizumab
- CYP3A inducers
- Systemic immunostimulatory agents (including, but not limited to, interferons and IL 2) are prohibited within 4 weeks or five drug elimination half-lives (whichever is longer) prior to initiation of study treatment and during study treatment because these agents could potentially increase the risk for autoimmune conditions when given in combination with atezolizumab.
- Grapefruit or grapefruit juice
- 5  $\alpha$ -reductase inhibitors (e.g., finasteride, dutasteride)

For patients in Arms B and C only:

- Systemic glucocorticoids or other immunosuppressive drugs (for any purpose other than to modulate symptoms from a drug-related AE of immunologic etiology - Refer to Section 6 for applicable adjustment of protocol therapy).
- (If precluded by local regulations) live vaccines should not be given for 120 days after the last dose of checkpoint inhibitor immunotherapy is administered.

**NOTE:**

Use of strong CYP3A inhibitors is discouraged unless medically unavoidable. Introduction of treatment with a strong inhibitor may be considered on a case-by-case basis and only after consultation with the Sponsor-Investigator. (*use caution with moderate [e.g., ciprofloxacin] or weak [e.g., ranitidine] inhibitors*). Refer to Section 6.2 for dosing modification of abemaciclib.

**The following medications and treatments are permitted while the patient is receiving protocol therapy:**

- Ongoing androgen deprivation therapy (e.g., LHRH agonist/antagonist)
- Prophylactic or therapeutic anticoagulation therapy (such as warfarin at a stable dose or low-molecular-weight heparin)
- Megestrol acetate administered as an appetite stimulant
- Vaccinations (such as, influenza, SARS-CoV-2)
- Live, attenuated vaccines are not permitted
  - Physiologic doses of prednisone  $\leq$ 10 mg (or equivalent) per day
  - Prophylactic corticosteroids to avoid allergic or other adverse reactions (e.g., known IV contrast allergy or prior to transfusions)
  - Physiologic doses of corticosteroids (subject to discussion and approval of Sponsor-Investigator)
  - Intermittent inhaled steroids or local injection of corticosteroids (subject to discussion and approval of Sponsor-Investigator)
  - Bisphosphonates/RANKL inhibitors. Starting bisphosphonates while on study, if indicated, is also allowed.

#### **5.4 Criteria for Taking a Participant Off Protocol Therapy**

Duration of therapy will depend on individual response, evidence of disease progression and tolerance. In the absence of treatment delays due to adverse event(s), treatment may continue indefinitely or until one of the following criteria applies:

- Disease progression by PCWG3 criteria (81), including clinical progression. Patients should not be discontinued from study therapy for PSA progression alone. PCWG3 criteria allow treatment beyond radiographic progression if the treating physician feels that the patient is continuing to derive clinical benefit from therapy, and the patient will continue until felt to be “no longer clinically benefiting” (NLCB). Patients in Arm B and the combination cohort of Arm C can be treated beyond progression per criteria in section 5.8.
- Intercurrent illness that prevents further administration of treatment
- Unacceptable adverse event(s)
- Participant demonstrates an inability or unwillingness to comply with the oral medication regimen and/or documentation requirements

- Participant decides to withdraw from the protocol therapy
- General or specific changes in the participant's condition render the participant unacceptable for further treatment in the judgment of the treating investigator

Participants will be removed from the protocol therapy when any of these criteria apply. The reason for removal from protocol therapy, and the date the participant was removed, must be documented in the case report form (CRF). Alternative care options will be discussed with the participant.

When a participant is removed from protocol therapy and/or is off of the study, the participant's status must be updated in OnCore in accordance with [REGIST-OP-1](#).

## 5.5 Duration of Follow Up

After treatment discontinuation, patients will be followed every 3 months for 24 months or until death, whichever occurs first. Participants removed from protocol therapy for unacceptable adverse event(s) will be followed until resolution or stabilization of the adverse event and for PSA and/or radiographic progression until a new treatment is started, the patient withdraws from study procedures, or death.

## 5.6 Criteria for Taking a Participant Off Study

Patients can be taken off study at any time at their own request, or they may be withdrawn at the discretion of the investigator for safety, behavioral or administrative reasons. The reason(s) for discontinuation from study will be documented and may include:

- Development of second malignancy (except for basal cell carcinoma or squamous cell carcinoma of the skin) that requires treatment, which would interfere with this study;
- Patient withdraws consent (termination of treatment AND follow-up);
- Loss of ability to freely provide consent through imprisonment or involuntary incarceration for treatment;
- Physician discretion (e.g., noncompliance or other circumstance);
- Lost to Follow-up;
- Termination of the study by Sponsor-Investigator or FDA;
- Patient completes protocol treatment and follow-up criteria.
- Death

Document in the source the reason for ending protocol therapy and the date the patient was removed from treatment. All patients who discontinue treatment should comply with protocol specific follow-up procedures as outlined in Section 10. The only exception to this requirement is when a subject withdraws consent for all study procedures or loses the ability

to consent freely.

The reason for taking a participant off study, and the date the participant was removed, must be documented in the case report form (CRF). In addition, the study team will ensure the participant's status is updated in OnCore in accordance with [REGIST-OP-1](#).

## **5.7 Patient Replacement**

Patients who have been registered and receive no protocol therapy will be replaced.

Patients who receive local intervention (e.g., palliative radiation) may be considered not evaluable. These patients may subsequently be assigned a conservative censoring or progression date.

## **5.8 Treatment Beyond Progression**

Accumulating evidence indicates a minority of subjects treated with immunotherapy may derive clinical benefit despite initial evidence of PD.

Subjects treated in C will be permitted to continue study treatment beyond initial RECISTv1.1 defined PD, assessed by the investigator, as long as they meet the following criteria:

- Investigator determined clinical benefit
- Tolerance of study drug
- Stable performance status
- Treatment beyond progression will not delay an imminent intervention to prevent serious complications of disease progression (e.g., CNS metastases)

## **6. DOSING DELAYS/DOSE MODIFICATIONS**

Dose delays and modifications will be made as indicated in the following table(s). The descriptions and grading scales found in the revised NCI Common Terminology Criteria for Adverse Events (CTCAE) version 5.0 will be utilized for dose delays and dose modifications. A copy of the CTCAE version 5.0 can be downloaded from the CTEP website [http://ctep.cancer.gov/protocolDevelopment/electronic\\_applications/ctc.htm](http://ctep.cancer.gov/protocolDevelopment/electronic_applications/ctc.htm).

Any patient who receives protocol treatment will be evaluable for toxicity. Each patient will be assessed for the development of toxicity according to the Study Calendar (Section 10). Toxicity will be assessed according to the NCI Common Terminology Criteria for Adverse Events (CTCAE), version 5.0. Dose adjustments should be made according to the system showing the greatest degree of toxicity. The dose delays and modifications described here are requirements, but re-escalation of abemaciclib dose is permitted per discretion of the treating investigator if there is improvement in the adverse event for which the dose was initially reduced. Investigators are encouraged to contact the Sponsor-Investigative team with any questions.

**Table 4. Abemaciclib Dosing Modifications**

Abemaciclib Dosing Modifications		
Dose Level	Monotherapy	Combination therapy
1	200mg BID	150mg BID
-1	150mg BID	100mg BID
-2	100mg BID	50mg BID
-3	50mg BID	Discontinue

## **6.1 Risks Associated with Atezolizumab and Guidelines for Management of Adverse Events Associated with Atezolizumab**

Toxicities associated or possibly associated with atezolizumab treatment should be managed according to standard medical practice. Additional tests, such as autoimmune serology or biopsies, should be used to evaluate for a possible immunogenic etiology.

Although most immune-mediated adverse events observed with atezolizumab have been mild and self-limiting, such events should be recognized early and treated promptly to avoid potential major complications. Discontinuation of atezolizumab may not have an immediate therapeutic effect, and in severe cases, immune-related toxicities may require acute management with topical corticosteroids, systemic corticosteroids, or other immunosuppressive agents.

The following are general recommendations for management of any other adverse events that may occur and are not specifically listed in the following subsections.

- Patients and family caregivers should receive timely and up-to-date information about immunotherapies, their mechanism of action, and the clinical profile of possible immune-related adverse events prior to initiating therapy and throughout treatment and survival follow-up. There should be a high level of suspicion that new symptoms are treatment related.
- In general, atezolizumab therapy should be continued with close monitoring for Grade 1 toxicities, with the exception of some neurologic toxicities.
- Consider holding atezolizumab for most Grade 2 toxicities and resume when symptoms and/or laboratory values resolve to Grade 1 or better. Corticosteroids (initial dose of 0.5-1 mg/kg/day of prednisone or equivalent) may be administered.
- For Grade 2 recurrent or persistent (lasting for more than 5 days) events, treat as a Grade 3 event.
- Hold atezolizumab for Grade 3 toxicities and initiate treatment with high-dose corticosteroids (1-2 mg/kg/day prednisone or equivalent). Corticosteroids should be tapered over 1 month to 10 mg/day oral prednisone or equivalent, before atezolizumab can be resumed. If symptoms do not improve within 48 to 72 hours of high-dose corticosteroid use, other immunosuppressants may be offered for some toxicities.
- In general, Grade 4 toxicities warrant permanent discontinuation of atezolizumab treatment, with the exception of endocrinopathies that are controlled by hormone replacement therapy.

The investigator should consider the benefit–risk balance for a given patient prior to further administration of atezolizumab. In patients who have met the criteria for permanent discontinuation, resumption of atezolizumab may be considered if the patient is deriving benefit and has fully recovered from the immune-mediated event. The decision to re-challenge patients with atezolizumab should be based on investigator’s assessment of benefit–risk and documented by the investigator.

## **DOSE MODIFICATIONS**

There will be no dose modifications for atezolizumab in this study.

## **TREATMENT INTERRUPTION**

Atezolizumab treatment may be temporarily suspended in patients experiencing toxicity considered to be related to study treatment. If corticosteroids are initiated for treatment of the toxicity, they must be tapered over  $\geq 1$  month to the equivalent of  $\leq 10$  mg/day oral prednisone before atezolizumab can be resumed. If atezolizumab is withheld for  $> 12$  weeks after event onset, the patient will be discontinued from atezolizumab. However, atezolizumab may be withheld for  $> 12$  weeks to allow for patients to taper off corticosteroids prior to resuming treatment. Atezolizumab can be resumed after being withheld for  $> 12$  weeks if the patient is likely to derive clinical benefit. The decision to re-challenge patients with atezolizumab should be based on investigator's assessment of benefit–risk and documented by the investigator. Atezolizumab treatment may be suspended for reasons other than toxicity (e.g., surgical procedures). The acceptable length of treatment interruption must be based on an assessment of benefit–risk by the investigator and in alignment with the protocol requirements for the duration of treatment and documented by the investigator.

## **PULMONARY EVENTS**

Dyspnea, cough, fatigue, hypoxia, pneumonitis, and pulmonary infiltrates have been associated with the administration of atezolizumab. Patients will be assessed for pulmonary signs and symptoms throughout the study and will have computed tomography (CT) scans of the chest performed at every tumor assessment.

All pulmonary events should be thoroughly evaluated for other commonly reported etiologies such as pneumonia or other infection, lymphangitic carcinomatosis, pulmonary embolism, heart failure, chronic obstructive pulmonary disease, or pulmonary hypertension. Management guidelines for pulmonary events are provided in Table 5.

**Table 5. Management Guidelines for Pulmonary Events, Including Pneumonitis**

Event	Management
Pulmonary Event, Grade 1	
 
Continue atezolizumab and monitor closely.
 
Re-evaluate on serial imaging.
 
Consider patient referral to pulmonary specialist.
 
For Grade 1 pneumonitis, consider withholding atezolizumab.
 

Pulmonary Event, Grade 2	
 
Withhold atezolizumab for up to 12 weeks after event onset.a
 
Refer patient to pulmonary and infectious disease specialists and consider bronchoscopy or BAL.
 
Initiate treatment with corticosteroids equivalent to 1–2 mg/kg/day oral prednisone.
 
If event resolves to Grade 1 or better, resume atezolizumab.b
 
If event does not resolve to Grade 1 or better while withholding atezolizumab, permanently discontinue atezolizumab.c
 
For recurrent events, or events with no improvement after 48–72 hours of corticosteroids, treat as a Grade 3 or 4 event.
 
•
 

Pulmonary Event, Grade 3 or 4	
 
Permanently discontinue abemaciclib and atezolizumab and contact Sponsor-Investigator.
 
Oral or IV broad-spectrum antibiotics should be administered in parallel to the immunosuppressive treatment.
 
Bronchoscopy or BAL is recommended.
 
Initiate treatment with corticosteroids equivalent to 1–2 mg/kg/day IV methylprednisolone.
 
If event does not improve within 48 hours after initiating corticosteroids, consider adding an immunosuppressive agent.
 
If event resolves to Grade 1 or better, taper corticosteroids over <math>\geq</math> 1 month.
 

BAL = bronchoscopic alveolar lavage.a Atezolizumab may be withheld for a longer period of time (i.e.,  $> 12$  weeks after event onset) to allow for corticosteroids (if initiated) to be reduced to the equivalent of  $\leq 10$  mg/day oral prednisone. The acceptable length of the extended period of time must be based on an assessment of benefit–risk by the investigator and in alignment with the protocol requirements for the duration of treatment and documented by the investigator.

b If corticosteroids have been initiated, they must be tapered over  $\geq$  1 month to the equivalent of  $\leq 10$  mg/day oral prednisone before atezolizumab can be resumed.

c Resumption of atezolizumab may be considered in patients who are deriving benefit and have fully recovered from the immune-mediated event. The decision to re–challenge patients with atezolizumab should be based on investigator's assessment of benefit–risk and documented by the investigator (or appropriate delegate).

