**Table 21. Interstitial lung disease (ILD) or Pneumonitis Events**

Interstitial lung disease (ILD) or Pneumonitis Events	Management
(management overview)	
Interstitial lung disease (ILD) / pneumonitis has been identified as an adverse drug reaction for abemaciclib. Adverse events reported included events such as interstitial lung disease, pneumonitis, obliterative bronchiolitis, organizing pneumonia, pulmonary fibrosis. The majority of events were Grade 1 or Grade 2 with serious cases and fatal events reported.
 
Patients should be asked to report any new or worsening pulmonary symptoms such as dyspnea, cough and fever; these symptoms should be investigated and treated as per local clinical practice and/or guidelines (including corticosteroids as appropriate). Investigations may include imaging such as high resolution computer tomography (HRCT), bronchoalveolar lavage (BAL), and biopsy as clinically indicated.

Grade 1, development of radiological or PFT changes suggestive of pneumonitis and have few or no symptoms	
 
Perform high-resolution CT scan (defined as slice thickness of 1 to 1.25mm and use of high special frequency algorithm).
 
If after initial workup, the patient does not meet CTCAE 5.0 criteria for grade <math>\geq 2</math> pneumonitis/ILD (symptomatic or needing medical intervention), treatment may be continued
 
The patient will be monitored closely with high-resolution CT scans and PFTs every 8 weeks until resolution of Grade 1 pneumonitis or until worsening to grade <math>\geq 2</math> pneumonitis/ILD at which time the treatment must be withheld per protocol.
 
Consider patient referral to pulmonary specialist.
 

Grade 2, 3 or 4	
 
Permanently discontinue abemaciclib and atezolizumab and contact Sponsor-Investigator.
 
Referral to pulmonary specialist is recommended with consideration of bronchoscopy or BAL.
 
Initiate treatment with 1-2 mg/kg/day oral prednisone or equivalent.
 
If event does not improve within 48 hours after initiating corticosteroids, consider adding an immunosuppressive agent.
 
If event resolves to Grade 1 or better, taper corticosteroids over <math>\geq 1</math> month.
 
Patients who develop <math>\geq</math> grade 2 pneumonitis/ILD must withdraw from further study treatment
 

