5. Data on adverse events will be collected from the time of the initial study drug administration through 100 days after the last dose of study drug. Data will also be collected regarding any serious adverse event that occurs more than 100 days after the last dose of study drug(s) and is considered related to study drug.
6. Only required for patients receiving atezolizumab-containing regimens on cycle 1 day 1 and every 3 cycles, otherwise only as clinically indicated.
7. MRI or CT of abdomen and pelvis along with chest CT with or without IV contrast. Brain CT or MRI with (preferred) or without IV contrast as indicated. To be assessed every 3 cycles (-1 week window) beginning with C4D1, i.e. within 1 week of planned C4D1, C7D1, etc. If the initiation of cycle 4, cycle 7, etc. is planned to be delayed (for toxicity management, scheduling, or any other reason), then imaging should be delayed as well. However, if imaging studies are performed and intercurrent toxicities preclude initiation of C4D1, C7D1, etc. within 1 week, the imaging does not need to be repeated prior to eventual initiation of the next treatment cycle.
8. PFTs include spirometry, lung volumes and DLCO. If PFTs after 3 months of trial therapy do not meet criteria for grade 1 or higher pneumonitis/ILD, then further monitoring PFTs are not required. If a patient develops grade 1 or higher pneumonitis/ILD, PFTs should be obtained every 8 weeks until resolution; if a patient develops grade 2 or higher pneumonitis/ILD, they must be discontinued from trial therapy.
9. Research blood at time of screening is whole blood collected in EDTA tube to isolate buffy coat for germline DNA, at subsequent time points are 2  $\times$  10mL serum tubes for exosome analysis, and 1  $\times$  10mL Streck® tube for cfDNA analysis. Collect C1D1 prior to administration of protocol therapy and after completing 2 cycles of protocol therapy  $\pm$  14 days. Collection also at C6D1, C9D1, and C12D1  $\pm$  3 business days.
10. May be collected and submitted up to 30 days after progression and prior to any intervening treatment. If progression collection is within 14 days of prior correlative blood collection, these research samples do not need to be collected.
11. Refer to section 9.1 for specimen requirement details.
12. Required after completing 2 cycles of protocol therapy  $\pm$  7 days, for all patients. Refer to section 9.1 for specimen requirement details.

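### Grade 2 pneumonitis on atezolizumab: Table 5 resumes the drug after resolution, Table 21 and study calendar note 8 stop it for good, and no text says which governs

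*Combined protocol and SAP*

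**What the plan says.** The opening of Section 6 makes its delay and modification rules mandatory. Two of its tables then address the same event.

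- Section 6.1 is headed "Table 5. Management Guidelines for Pulmonary Events, Including Pneumonitis". Its grade 2 row withholds atezolizumab for up to 12 weeks, and then: "If event resolves to Grade 1 or better, resume atezolizumab". Permanent discontinuation follows only if the event fails to resolve, and footnote c softens even that: "Resumption of atezolizumab may be considered in patients who are deriving benefit and have fully recovered from the immune-mediated event".
- Section 6.2 Table 21, on ILD and pneumonitis, puts grade 2 in one row with grades 3 and 4: "Permanently discontinue abemaciclib and atezolizumab and contact Sponsor-Investigator". It adds that patients at or above "grade 2 pneumonitis/ILD must withdraw from further study treatment".
- Section 10, Table 27 note 8, on pulmonary function tests, says: "if a patient develops grade 2 or higher pneumonitis/ILD, they must be discontinued from trial therapy".

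Two general passages in Section 6.1 also bear on this. The paragraph before Dose Modifications lets the investigator consider restarting atezolizumab in a patient who met permanent-discontinuation criteria and has fully recovered. The Treatment Interruption paragraph allows a restart after a hold of more than 12 weeks if benefit is likely.

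**The concern.** A site with an atezolizumab patient whose grade 2 pneumonitis has settled to grade 1 is told both to restart and never to restart. Either action breaches a rule written as mandatory, and two sites could treat identical events in opposite ways while each cites the protocol.

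The plan guards closely against pneumonitis. It excludes patients on smoking history, lung history and pulmonary function, and it repeats pulmonary function testing on treatment. Section 2.3.3 cites a pooled analysis suggesting higher pneumonitis risk after radiation, while Section 3.3.18 waives the thoracic-radiation exclusion for Arm C atezolizumab monotherapy patients. So the group facing the conflicting rules may include patients with a risk factor that the plan itself names. Following Table 5 would re-expose a patient whom two other places in the protocol say must come off treatment.

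**Working it through.** There is no planned figure to reproduce. The check is a comparison of texts, followed by a bound on how many patients could be affected.

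**1. Instructions by grade for a patient on atezolizumab**

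| Event | Table 5 | Table 21 and note 8 | Compatible? |
|---|---|---|---|
| Grade 2, resolves to grade 1 or better | Hold, then resume | Permanent stop, withdraw | No |
| Grade 2, does not resolve | Permanent stop, re-challenge possible under footnote c | Permanent stop, withdraw | Not if re-challenged |
| Grade 3 or 4 | Permanent stop of both drugs | Permanent stop, withdraw | Yes |

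Within the event tables, the clash is confined to grade 2.

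**2. Can the texts be reconciled?**

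- *Table 5 covers only other pulmonary events.* No. Its title includes pneumonitis, and its grade 1 row has an instruction specific to pneumonitis.
- *Table 21 concerns abemaciclib only.* Its place in Section 6.2 suggests this, but it orders atezolizumab stopped by name. Note 8 has no arm or drug limit, whereas note 6 of the same calendar states one where it is meant: "Only required for patients receiving atezolizumab-containing regimens on cycle 1 day 1 and every 3 cycles".
- *The 28-day delay limit in Section 5.1 ends treatment anyway.* No. That limit yields to more specific provisions, and Table 5 provides for up to 12 weeks.
- *The DLT definition in Section 7.3 settles it.* No. It says when grade 2 pneumonitis counts as a DLT, not whether the drug restarts.
- *An order of precedence is given.* None was found.

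**3. Patients who could be affected**

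- Arm C atezolizumab monotherapy: at most 5 (Section 1.1).
- Arm B: 8 treated, with two grade 5 sepsis events (Section 1.1), so at most 8 − 2 = 6.
- Total: 0 to 5 + 6 = 11. The number still on the drug is not stated.

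**4. Chance that the conflict arises**

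The documents give no grade 2 pneumonitis rate. Assume p between 1% and 5%. With n patients at risk, P(at least one case) = 1 − (1 − p)^n, and expected cases = n × p.

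| n | P at p = 0.01 | P at p = 0.05 | Expected cases |
|---|---|---|---|
| 0 | 0 | 0 | 0 |
| 5 | 1 − 0.99^5 = 4.9% | 1 − 0.95^5 = 22.6% | 0.05 to 0.25 |
| 11 | 1 − 0.99^11 = 10.5% | 1 − 0.95^11 = 43.1% | 0.11 to 0.55 |

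The highest figure needs both the top assumed rate and all 11 patients still on atezolizumab.

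**The case against.** The best reply is that a lighter rule for atezolizumab monotherapy may be deliberate. Sections 3.1.9 and 3.3.18 relax the transaminase, transfusion and thoracic-radiation criteria for that group alone. Section 7.3 counts grade 2 pneumonitis as a DLT only if it has not improved within 14 days. Table 21 sits under abemaciclib management, and note 8 is a lung-function footnote that may merely restate Table 21. This stands in part: a reader might infer that note 8 proves the strict rule was meant for atezolizumab monotherapy, but it is strong evidence, not proof. It does not remove the conflict, because no such limit is written in Table 21 or note 8.

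Two other stronger readings are not supported.

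- A reader might infer that Table 21 contradicts itself, since its grade 1 row speaks of worsening to grade 2 or higher "pneumonitis/ILD at which time the treatment must be withheld per protocol" while the next row discontinues permanently. Withholding first and then discontinuing, as the next row directs, are compatible.
- A reader might carry the two pneumonitis deaths in Section 2.3.3 over to these patients. Those deaths were on abemaciclib, pembrolizumab and anastrozole in breast cancer. The same section reports numerically less severe pneumonitis with anti-PD-L1 agents, and none of grade 3 or higher for atezolizumab monotherapy in a urothelial carcinoma trial. The deaths explain the plan's caution but do not measure the risk here.

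It is also fair to say that combination enrolment has closed, and that Table 21 and note 8 agree for patients on abemaciclib alone.

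**Conclusion.** The inconsistency is real and in current text. For grade 2 pneumonitis on atezolizumab that resolves, the protocol requires both resumption and permanent withdrawal. It should be corrected, because following Table 5 breaches a safety rule stated in two other places and the cure is wording only.

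Its size is modest: 0 to 11 patients, with none affected if nobody remains on atezolizumab. The event probabilities rest on an assumed 1% to 5% rate that the documents do not supply. A reader might infer some threat to the efficacy conclusions, but this point changes no power, error rate or efficacy analysis. Which rule the sponsor intended for atezolizumab monotherapy cannot be settled from the documents. The stricter one looks more likely: Table 5's grade 3 or 4 row names abemaciclib and carries no re-challenge footnote, which suggests that this row was adapted to the trial and the grade 2 row was not. That is an inference.

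**What to change.** If the strict rule is intended:

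1. In Table 5, limit the grade 2 resume instruction and footnote c to pulmonary events other than pneumonitis/ILD.
2. Add a Table 5 row: pneumonitis/ILD of grade 2 or higher means permanent discontinuation, as in Table 21 and Table 27 note 8.
3. Except pneumonitis/ILD of grade 2 or higher from both general re-challenge permissions in Section 6.1: the paragraph before Dose Modifications and the Treatment Interruption paragraph. Otherwise the first of these would let back in a patient whom Table 5 had just stopped.

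If the sponsor intends resumption on atezolizumab monotherapy, it should leave Table 5 in force for that regimen and expressly limit Table 21 and note 8 to abemaciclib-containing regimens.

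Replacing the word withheld in Table 21's grade 1 row would help clarity but is optional.

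The cost is a wording amendment, with no new visit, procedure or patient. The downside of the strict rule is that a patient benefiting from atezolizumab whose grade 2 pneumonitis resolves could not restart it.
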